##### Events Meeting the AE Definition

- Any abnormal laboratory test results (hematology or clinical chemistry) or other safety assessments (for example, electrocardiogram, radiological scans, vital signs measurements), including those that worsen from baseline, considered clinically significant in the medical and scientific judgment of the investigator (that is, not related to progression of underlying disease).
- Exacerbation of a chronic or intermittent pre-existing condition including either an increase in frequency and/or intensity of the condition.
- New condition detected or diagnosed after study intervention administration even though it may have been present before the start of the study.
- Signs, symptoms, or the clinical sequelae of a suspected drug-drug interaction.
- Signs, symptoms, or the clinical sequelae of a suspected overdose of either study intervention or a concomitant medication. Overdose per se will not be reported as

an AE/SAE unless it is an intentional overdose taken with possible suicidal/self-harming intent. Such overdoses should be reported regardless of sequelae.

- Lack of efficacy or failure of expected pharmacological action per se will not be reported as an AE or SAE. Such instances will be captured in the efficacy assessments. However, the signs, symptoms, and/or clinical sequelae resulting from lack of efficacy will be reported as AE or SAE if they fulfill the definition of an AE or SAE.

Events NOT Meeting the AE Definition

 
• Any clinically significant abnormal laboratory findings or other abnormal safety assessments that are associated with the underlying disease, unless judged by the investigator to be more severe than expected for the participant’s condition.
 
• The disease/disorder being studied or expected progression, signs, or symptoms of the disease/disorder being studied, unless more severe than expected for the participant’s condition.
 
• Medical or surgical procedure (for example, endoscopy, appendectomy): the condition that leads to the procedure is the AE.
 
• Situations in which an untoward medical occurrence did not occur (social and/or convenience admission to a hospital).
 
• Anticipated day-to-day fluctuations of pre-existing disease(s) or condition(s) present or detected at the start of the study that do not worsen.
 

**10.3.2. Definition of SAE**

An SAE is defined as any untoward medical occurrence that, at any dose, meets one or more of the criteria listed:

a. Results in death

b. Is life-threatening
 
The term life-threatening in the definition of serious refers to an event in which the participant was at risk of death at the time of the event. It does not refer to an event, which hypothetically might have caused death, if it were more severe.

c. Requires inpatient hospitalization or prolongation of existing hospitalization
 
 
• In general, hospitalization signifies that the participant has been admitted to hospital or emergency ward (usually involving at least an overnight stay) for observation and/or treatment that would not have been appropriate in the physician’s office or outpatient setting. Complications that occur during hospitalization are AEs. If a complication prolongs hospitalization or fulfills any other serious criteria, the event is serious. When in doubt as to whether hospitalization occurred or was necessary, the AE should be considered serious.
 

 
• Hospitalization for elective treatment of a pre-existing condition that did not worsen from baseline is not considered an AE.
 

d. Results in persistent disability/incapacity
 
 
• The term disability means a substantial disruption of a person’s ability to conduct normal life functions.
 
• This definition is not intended to include experiences of relatively minor medical significance such as uncomplicated headache, nausea, vomiting, diarrhea, influenza, and accidental trauma (for example, sprained ankle) which may interfere with or prevent everyday life functions but do not constitute a substantial disruption.
 

e. Is a congenital anomaly/birth defect
 
 
• Abnormal pregnancy outcomes (for example, spontaneous abortion, fetal death, stillbirth, congenital anomalies, ectopic pregnancy) are considered SAEs.
 


f. Other situations:
 
 
• Medical or scientific judgment should be exercised by the investigator in deciding whether SAE reporting is appropriate in other situations such as important medical events that may not be immediately life-threatening or result in death or hospitalization but may jeopardize the participant or may require medical or surgical intervention to prevent one of the other outcomes listed in the above definition. These events should usually be considered serious.
 
• Examples of such events include invasive or malignant cancers, intensive treatment in an emergency room or at home for allergic bronchospasm, blood dyscrasias or convulsions that do not result in hospitalization, or development of drug dependency or drug abuse.
 

g. Resulted in medical or surgical intervention to prevent life-threatening illness or injury or permanent impairment to a body structure or a body function.

**10.3.3. Definition of Product Complaints**

Product Complaint

 
• A PC is any written, electronic, or oral communication that alleges deficiencies related to the identity, quality, durability, reliability, safety, effectiveness or performance of a study intervention. When the ability to use the study intervention safely is impacted, the following are also PCs:               
 
○ Deficiencies in labeling information, and
 
○ Use errors for device or drug-device combination products due to ergonomic design elements of the product.
 
 
 

- Product complaints related to study interventions used in clinical trials are collected to ensure the safety of participants, monitor quality, and to facilitate process and product improvements.
- Investigators will instruct participants to contact the site as soon as possible if he or she has a PC or problem with the study intervention so that the situation can be assessed.
- An event may meet the definition of both a PC and an AE/SAE. In such cases, it should be reported as both a PC and as an AE/SAE.

#### 10.3.4. Recording and Follow-Up of AE and/or SAE and Product Complaints

##### AE, SAE, and Product Complaint Recording

- When an AE/SAE/PC occurs, it is the responsibility of the investigator to review all documentation (for example, hospital progress notes, laboratory reports, and diagnostics reports) related to the event.
- The investigator will then record all relevant AE/SAE/PC information in the participant's medical records, in accordance with the investigator's normal clinical practice. AE/SAE information is reported on the appropriate CRF page and PC information is reported on the PC Form.
  - NOTE: An event may meet the definition of both a PC and an AE/SAE. In such cases, it should be reported as both a PC and as an AE/SAE.
- It is **not** acceptable for the investigator to send photocopies of the participant's medical records to Sponsor or designee in lieu of completion of the CRF page for AE/SAE and the PC Form for PCs.
- There may be instances when copies of medical records for certain cases are requested by Sponsor or designee. In this case, all participant identifiers, with the exception of the participant number, will be redacted on the copies of the medical records before submission to Sponsor or designee.
- The investigator will attempt to establish a diagnosis of the event based on signs, symptoms, and/or other clinical information. Whenever possible, the diagnosis (not the individual signs/symptoms) will be documented as the AE/SAE.

##### Assessment of Intensity

The investigator will make an assessment of intensity for each AE and SAE reported during the study and assign it to one of the following categories:

- **Mild:** A type of adverse event that is usually transient and may require only minimal treatment or therapeutic intervention. The event does not generally interfere with usual activities of daily living.
- **Moderate:** A type of adverse event that is usually alleviated with additional specific therapeutic intervention. The event interferes with usual activities of daily living, causing discomfort but poses no significant or permanent risk of harm to the research participant.

- Severe: A type of adverse event that interrupts usual activities of daily living, or significantly affects clinical status, or may require intensive therapeutic intervention. An AE that is assessed as severe should not be confused with a SAE. Severe is a category utilized for rating the intensity of an event; and both AEs and SAEs can be assessed as severe.  
An event is defined as “serious” when it meets at least one of the predefined outcomes as described in the definition of an SAE, NOT when it is rated as severe.

### Assessment of Causality

- The investigator is obligated to assess the relationship between study intervention and each occurrence of each AE/SAE. The investigator will use clinical judgment to determine the relationship/
- A “reasonable possibility” of a relationship conveys that there are facts, evidence, and/or arguments to suggest a causal relationship, rather than a relationship cannot be ruled out.
- Alternative causes, such as underlying disease(s), concomitant therapy, and other risk factors, as well as the temporal relationship of the event to study intervention administration will be considered and investigated.
- The investigator will also consult the IB in their assessment.
- For each AE/SAE, the investigator **must** document in the medical notes that he/she has reviewed the AE/SAE and has provided an assessment of causality.
- There may be situations in which an SAE has occurred and the investigator has minimal information to include in the initial report to Sponsor or designee. However, it is very important that the investigator always make an assessment of causality for every event before the initial transmission of the SAE data to Sponsor or designee.
- The investigator may change their opinion of causality in light of follow-up information and send a SAE follow-up report with the updated causality assessment.
- The causality assessment is one of the criteria used when determining regulatory reporting requirements.

### Follow-up of AEs and SAEs

- The investigator is obligated to perform or arrange for the conduct of supplemental measurements and/or evaluations as medically indicated or as requested by Sponsor or designee to elucidate the nature and/or causality of the AE or SAE as fully as possible. This may include additional laboratory tests or investigations, histopathological examinations, or consultation with other health care professionals.

- If a participant dies during participation in the study or during a recognized follow-up period, the investigator will provide Sponsor or designee with a copy of any post-mortem findings including histopathology.

### 10.3.5. Reporting of SAEs

- | SAE Reporting via Paper Form   |
|---|
| 
 
• Facsimile transmission of the SAE paper form is the preferred method to transmit this information to the medical monitor or the SAE coordinator.
 
• Initial notification via telephone does not replace the need for the investigator to complete and sign the SAE CRF pages within the designated reporting time frames.
 
• Contacts for SAE reporting can be found in SAE form.
 
 |

### 10.3.6. Regulatory Reporting Requirements

- | SAE Regulatory Reporting  |
|--|
| 
 
• Prompt notification by the investigator to the sponsor of a SAE is essential so that legal obligations and ethical responsibilities towards the safety of participants and the safety of a study intervention under clinical investigation are met.
 
• The sponsor has a legal responsibility to notify both the local regulatory authority and other regulatory agencies about the safety of a study intervention under clinical investigation. The sponsor will evaluate the reported SAEs, including confirmation of relatedness and assessment of expectedness. The sponsor has processes for safety reports for identification, recording, and expedited reporting of suspected unexpected serious adverse reactions according to local regulatory requirements. The sponsor will comply with country-specific regulatory requirements relating to safety reporting to the regulatory authority, Institutional Review Boards (IRB)/Independent Ethics Committees (IEC), and investigators.
 
• An investigator who receives an investigator safety report describing a SAE or other specific safety information (for example, summary or listing of SAEs) from the sponsor will review and then file it along with the IB and will notify the IRB/IEC, if appropriate according to local requirements.
 
 |

## 10.4. Appendix 4: Contraceptive and Barrier Guidance

### 10.4.1. Definitions

#### Women of child-bearing potential (WOCBP)

Females are considered WOCBP if they have had at least 1 cycle of menses.

Any amount of spotting or bleeding should be considered menarche.

#### Women not of child-bearing potential (WNOCBP)

- females are considered WNOCBP if they have a congenital anomaly such as Mullerian agenesis,
- are infertile due to surgical sterilization, or
- are postmenopausal.

Examples of surgical sterilization include total hysterectomy, bilateral salpingo-oophorectomy, bilateral salpingectomy, or bilateral oophorectomy.

#### Postmenopausal

The postmenopausal state is defined as  $\geq 1$  year without a menstrual period confirmed by follicle stimulating hormone test.

### 10.4.2. Contraception Guidance

#### Guidance for WOCBP

This outlines the rules for WOCBP to ensure they do not become pregnant during the study.

WOCBP who are completely abstinent as their preferred and usual lifestyle, or in a same-sex relationship as their preferred and usual lifestyle:

Must...	Must not...
agree to either remain abstinent or stay in a same-sex relationship without sexual relationships with males	
 
• use periodic abstinence methods                             
 
○ calendar
 
○ ovulation
 
○ symptothermal, or
 
○ post-ovulation
 
 
 
• declare abstinence just for the duration of a trial, or
 
• use the withdrawal method
 

WOCBP who are NOT completely abstinent as their preferred and usual lifestyle, or NOT in a same-sex relationship as their preferred and usual lifestyle, must do the following:

Topic	Condition
Pregnancy testing	Have a negative serum test result at screening (or upon a participant that reaches menarche during the trial and is sexually active) followed by a negative urine result within 24 hours prior to treatment exposure. See the protocol SoA for subsequent pregnancy testing requirements.

Topic	Condition
Contraception	
Agree to use 1 highly effective method of contraception, or a combination of 2 effective methods of contraception.
 
These forms of contraception must be used for the duration of the study.

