### Brief Summary:

The purpose of this study is to measure percentage of participants achieving EASI-75 at Week 16 with lebrikizumab in adolescent and adult participants with skin of color and moderate-to-severe AD.

Study details include

- The planned study duration will be up to 38 weeks.
- The treatment duration will be up to 24 weeks.
- The visit frequency will be every 2 weeks for the first 2 visits, then every 4 weeks thereafter.

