#### Study Periods

This trial has 3 study periods:

- Screening (Visit 1: ≤30 days prior to baseline)
- Treatment (Visits 2-9: 24 weeks)
- Safety follow-up (Visit 801: approximately 12 weeks after last treatment)

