#### Sex and Contraceptive/Barrier Requirements

10. Male and/or female
  - a. No male contraception is required except in compliance with specific local government study requirements.
  - b. Female participants of child-bearing potential must agree to remain abstinent (refrain from heterosexual intercourse) or use a highly effective contraceptive method during the treatment period and for at least 18 weeks after the last dose of study drug. Women not of child-bearing potential (WNOCBP) may participate without any contraception requirements. For definitions of women of child-bearing potential (WOCBP) and WNOCBP, see Section 10.4, Appendix 4.

Contraceptive use by participants should be consistent with local regulations regarding the methods of contraception for those participating in clinical studies. For the contraception requirements of this protocol, see Section 10.4, Appendix 4.

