**Examples of different forms of contraception:**

Methods	Examples
Highly effective contraception (less than 1% failure rate)	
 
• female sterilization
 
• combination oral contraceptive pill
 
• progestin-only contraceptive pill (mini-pill)
 
• implanted contraceptives
 
• injectable contraceptives
 
• contraceptive patch (only women <198 pounds or 90 kg)
 
• total abstinence
 
• vasectomy, if only sexual partner
 
• fallopian tube implants, if confirmed by hysterosalpingogram
 
• combined contraceptive vaginal ring, or
 
• intrauterine devices
 

Effective contraception	
 
• male or female condoms with spermicide
 
• diaphragms with spermicide or cervical sponges
 
• barrier method with use of a spermicide                             
 
○ condom with spermicide
 
○ diaphragm with spermicide, or
 
○ female condom with spermicide
 
 
 
 
NOTE: The barrier method must include use of a spermicide (that is, condom with spermicide, diaphragm with spermicide, and female condom with spermicide) to be considered effective.

Methods	Examples
Ineffective forms of contraception	
 
• spermicide alone
 
• immunocontraceptives
 
• periodic abstinence
 
• fertility awareness (calendar method, temperature method, combination of above 2, cervical mucus, symptothermal)
 
• withdrawal
 
• post coital douche, and
 
• lactational amenorrhea
 

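### Inclusion criterion 10b and Appendix 4 set different contraception rules: Appendix 4 omits the 18 weeks after the last dose and accepts methods that 10b does not list

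*Protocol*

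**What the plan says.** Criterion 10b (Protocol Section 5.1) requires women of child-bearing potential to agree to abstinence or to "use a highly effective contraceptive method during the treatment period and for at least 18 weeks after the last dose of study drug". The same criterion then directs the reader elsewhere: "For the contraception requirements of this protocol, see Section 10.4, Appendix 4".

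Appendix 4 (Section 10.4.2) describes its scope as follows: "This outlines the rules for WOCBP to ensure they do not become pregnant during the study". For women who are not abstinent and not in a same-sex relationship as their usual lifestyle, the condition is "Agree to use 1 highly effective method of contraception, or a combination of 2 effective methods of contraception", followed by "These forms of contraception must be used for the duration of the study". The table of examples defines highly effective methods by a failure rate below 1% and lists effective methods in a separate row, starting with "male or female condoms with spermicide". No period after the last dose appears anywhere in Appendix 4.

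The study periods in Section 4.1 end with "Safety follow-up (Visit 801: approximately 12 weeks after last treatment". The synopsis states: "The planned study duration will be up to 38 weeks".

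**The concern.** Two current parts of the protocol govern the same obligation and differ in both duration and accepted methods. Because 10b itself names Appendix 4 as the place for the requirements, a site could reasonably treat Appendix 4 as complete. It might then tell a woman that contraception ends with her final visit, some weeks before the 10b period is over.

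The 18 weeks is not an isolated figure. Section 8.3.1 collects pregnancies for at least 18 weeks after the last dose. Section 6.7 uses the same period for overdose monitoring and ties it to the drug no longer being detectable.

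The schedule of activities has no pregnancy test at Visit 801; the last is at Week 24 or early discontinuation. After that point the contraception instruction is the main safeguard.

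The methods difference affects eligibility. Section 5 permits no waivers of enrollment criteria, and SAP Section 5.15 gives violation of the inclusion or exclusion criteria as an example of an important deviation.

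**Working it through.** **Inputs**

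- Period after the last dose in 10b: at least 18 weeks (Section 5.1).
- Last dose to Visit 801: about 12 weeks (Section 4.1), window ±7 days (Section 1.3).
- Last planned dose: Week 20 for Week 16 responders, Week 22 for inadequate responders (Section 1.3).
- Screening: at most 30 days, which is 30/7 = 4.3 weeks.
- Planned study duration: up to 38 weeks (Section 1.1).

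**Reproducing the plan's own figure.** Longest participation = screening + last dose + follow-up = 4.3 + 22 + 12 = 38.3 weeks. This matches the stated 38 weeks, so in the synopsis the study duration means one participant's time in the study.

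**Duration, individual reading.** Section 4.4 counts a participant as complete after the last scheduled procedure, which is Visit 801.

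- Shortfall = 18 − 12 = 6 weeks.
- With the ±7-day window: 18 − 13 = 5 weeks to 18 − 11 = 7 weeks.
- With the ±14-day window that Appendix 10 allows in exceptional circumstances: 18 − 14 = 4 weeks to 18 − 10 = 8 weeks.

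| Last dose | Visit 801 (Appendix 4 ends) | 10b ends | Gap |
|---|---|---|---|
| Week 20 | 20 + 12 = Week 32 | 20 + 18 = Week 38 | 6 weeks |
| Week 22 | 22 + 12 = Week 34 | 22 + 18 = Week 40 | 6 weeks |

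**Duration, whole-trial reading.** Section 4.4 also defines the end of the study by the last participant's last visit. Let Lmax be the date of the final participant's last dose, and set Addendum 3 aside. The trial ends at Lmax + 12 weeks. For a woman whose last dose is at L, 10b ends at L + 18 weeks. A gap exists only if L + 18 > Lmax + 12, that is, if L > Lmax − 6 weeks. Women who finish early would have to continue longer than 10b asks; those dosed in the final 6 weeks would fall short of it. This reading does not bring the texts into line either.

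**Methods, side by side.**

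| Method | 10b | Appendix 4 |
|---|---|---|
| Abstinence | accepted | accepted |
| One highly effective method | accepted | accepted |
| Two effective methods combined | not listed | accepted |

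Two effective methods cannot be read as one highly effective method, because Appendix 4 itself places them in separate classes.

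**The case against.** The strongest reply is that, on duration, Appendix 4 omits something rather than contradicts 10b. On the individual reading, a woman who follows 10b also satisfies Appendix 4, and nothing in Appendix 4 says she may stop before 10b allows. Section 5.1 admits participants only if every criterion is met, so she must have agreed to the 18 weeks at entry. A site would have to overlook a mandatory criterion for harm to follow.

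Much of this stands: the duration point is an omission, and 10b does bind at enrollment. It does not close the gap, for two reasons. The protocol has no clause saying which text prevails, while 10b sends the reader to Appendix 4. In addition, the schedule of activities refers sexually active girls who reach menarche during the trial to Appendix 4 alone. Before menarche they do not meet the Appendix 4 definition of child-bearing potential, so the 10b agreement would not have applied to them at entry. The text they are referred to contains no 18-week rule.

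The reply does not reach the methods difference. If Section 5.1 makes 10b decisive, a woman enrolled on two barrier methods under Appendix 4 has failed an entry criterion.

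It is also fair that the practical effect cannot be measured from these documents. What women are told depends on the consent form, which was not available. Participants entering Addendum 3 skip Visit 801 (SAP Section 4.1), and that addendum was not available either. The documents cite 18 weeks for drug detectability only in the overdose section.

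**Conclusion.** The concern holds. On methods the two texts conflict directly. On duration Appendix 4 leaves out the period after the last dose that 10b requires. The shortfall is about 6 weeks, or 5 to 7 with the normal visit window, if the study means the individual's participation; the 38-week figure in the synopsis supports that reading. On the whole-trial reading it is confined to women whose last dose falls within about 6 weeks of the final participant's.

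The duration point matters for non-abstinent women of child-bearing potential who finish at Visit 801 and use a method they can readily stop. The documents do not give their number. This is a participant-safety and eligibility inconsistency that should be corrected; it changes no endpoint, sample size or analysis.

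**What to change.** In Appendix 4, replace the duration sentence with one requiring contraception during the treatment period and for at least 18 weeks after the last dose of study drug. That matches 10b and agrees with the pregnancy reporting window in Section 8.3.1.

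Have the clinical team decide whether two effective methods in combination are acceptable, and print the same list in 10b and Appendix 4. If the option is removed, state how women already enrolled on it are to be handled. Check that the consent form agrees with the result.

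The cost is a wording amendment to Appendix 4, and to 10b if the two-method option is kept. It needs IRB/IEC approval before implementation (Section 10.1.1) and re-consent to any updated form (Section 10.1.3). If the option is dropped, some enrolled women may need to change method. No visits, tests or data collection are added.
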